13.0 Withdrawal of Subjects

13.1 Circumstances under which subjects would be withdrawn without their consent

All study subjects have the right to withdraw their consent at any time during the study. However, withdrawal of a subject from the study can occur at the direction of the PI or the sponsor. Reasons for physician directed withdrawal could include but are not limited to: the subject's not adhering to the study follow-up protocol, the subject enrolls in another study which conflicts with this study's primary or secondary endpoints, or if the physician deems it is in the patients best interest for safety or welfare of the subject to withdraw.

13.2 Procedures for Termination

When possible the coordinator should obtain written documentation from the subject that wishes to withdraw his/her consent for future follow-up and contacts. If written documentation is unable to be obtained, all information regarding the subject's withdrawal

must be recorded in the subject's medical record. In addition, the appropriate CRF's must be completed for the subject and clear documentation of the subject's withdrawal be provided to the sponsor.

13.3 Procedures for partial withdrawal

Subject withdrawal is unlikely because other than randomization to intra-operative wound treatment, all care will be provided in the standard fashion and follow-up requirements (30 day follow-up with the surgeon or his/her designee) will be the same regardless of participation in the study. However, if the subject for any reason chooses to withdraw from the study, procedure will be followed as in 13.2.

13.4 Lost to Follow-up

Every attempt will be made to have all subjects complete the follow-up schedule. A subject will not be considered lost to follow-up unless efforts to obtain compliance are unsuccessful. At minimum, three attempts by telephone via the most recent contact number should be made. If these efforts are unsuccessful, a certified letter from the PI should be sent to the subject's last known address. Attempts to contact the subject should be noted in the his/her medical record and on the study case report form.

14.0 Risks to Subjects

14.1 Foreseeable risks

Subjects in this study will be exposed to anesthetic, operative, and postoperative risks inherent to vascular surgery that requires groin incision.

- Anesthetic risk
Anesthesia will be provided per the surgeon's preference and will not expose subjects to additional risk beyond that experienced during routine vascular surgery.
- Procedural risks
Additional procedural risks will be nominal.
- Postoperative Risks
Routine postoperative care will be provided and will pose no additional risk to subjects in either arm of the study.
- Follow-up Risks
Standard intervals for follow-up will be employed and will pose no additional risk for subjects in either arm of the study
 - Clinical evaluation will be required at 30 days (25 -40) after surgery

14.2 Unforeseeable risks

Any serious adverse event leading to injury, illness or death of a subject not previously identified in nature, severity or degree of incidence in this protocol, literature or application (including a supplementary plan or application) that may be directly related to use of the device

15.0 Potential Benefits to Subjects

15.1 Potential benefits may be experienced in subjects randomized to:

Prevena Incision Management System

Patients randomized to Prevena may have lower rates of groin incision infection and be less likely to require additional wound care treatment or longer hospital length of stay, or readmission to the hospital within 30 days to manage infection. Need for home health care to manage wound infection may be lower and recuperation period shorter than if infection was to occur.

15.2 Potential benefits to hospital

Premptive use of Prevena may lower surgical incision infection rates and 30 day readmission rates for treatment of infected surgical incisions, key outcomes measures by which hospitals are evaluated. The associated reduction in surgical site infection rates may result in decreased spending, thus improving hospital contribution margin.

16.0 Vulnerable populations

16.1 Safeguards to protect the rights and welfare of vulnerable populations

Minors, pregnant women, prisoners or cognitively impaired adults will not be included in the study.

17.0 Community-Based Participatory Research

17.1 Community involvement in the design and conduct of the Study

The concept and design of the study was developed by the Principal Investigator in collaboration with members of the research team including co-investigators, study coordinators and a biostatistician. This project has the potential to change current standards of practice for surgical wound management in subjects who undergo vascular surgery that requires a groin incision. To the individual, this translates to a hospitalization less likely to be complicated by infection which equates to quicker recovery and positive hospital experience. Image is critical to hospitals in this competitive health care market as are quality outcomes such as low surgical infection rates and reduced hospital readmission. Both are likely to be associated with substantial financial savings and improved utilization of resources.

18.0 Sharing of Results with Subjects

18.1 Individual results of the clinical endpoint will be obvious to the subject and will be shared via verbal communication from the surgeon or his designee (resident, nurse practitioner, physician assistant). Results will be shared with the subject's primary care physician through written correspondence. Results of the study when available will be

shared verbally with the subject upon request.

19.0 Setting

19.1 Description of study site locations

The study will be conducted at 2 sites: Buffalo General Medical Center, Kaleida Health, and Erie County Medical Center (ECMC). The Veteran's Administration Medical Center of Buffalo (VAMC) may be added with an addendum if there is a need for additional numbers. This would require a separate IRB submission.

- The Buffalo General Medical Center is a ___ bed University of Buffalo Medical School affiliated Tertiary Care Center. The Medical center boasts a new state of the art Global Vascular Institute and is a key provider of vascular care to Western New Yorkers. Over _____ vascular procedures are completed annually by five board-certified vascular surgeons, including 2 academic surgeons and the Division Chief of the Division of Vascular Surgery, Department of Surgery, University of Buffalo Medical School, and an internationally known vascular surgeon, trained internationally. The medical center is the premiere training site for the University's Vascular Fellowship and Integrated Vascular Residency Programs accredited through the Accreditation Council of Graduate Medical Education.

19.2 Identification of potential study subjects

The nurse coordinator will identify potential study subjects through multiple- sources.

- The coordinator will monitor the office schedules of participating surgeons and identify patients having vascular surgery that requires groin incision as potential candidates.
 - The office staff of participating surgeons will be asked to notify the coordinator when scheduling a patient office visits for lower extremity intervention or aortic aneurysm repair likely to require a groin incision
- The coordinator will review the operating room schedule daily to identify potential subjects
- The coordinator will collaborate daily with the Vascular Fellow/resident to identify potential candidates on the Vascular Service or referred to the Vascular Service for surgery that may require groin incision.
 - Vascular Fellows/residents will be asked to notify the coordinator of potential study subjects

19.3 Location of Research procedures

Research procedures will be completed in the following areas

- Surgeon's exam room, patient hospital room or other private room in the hospital
Patients may be screened for eligibility, consent obtained and randomized to a study arm in the surgeon's office, patient hospital room or other private room in the hospital.
- Operating Room

- Prevena (3 units) and Dermabond are both readily available in the OR supply area. The coordinator will ensure that there continues to be an adequate supply to allow for randomization. Both products are also used for other procedures, both vascular and other surgical interventions.
- The Clinical coordinator's office, participating surgeon's office, medical record department, hospital surgical unit
These areas may be used for collecting and in-putting data.

The aforementioned precautions will be used to assure patient confidentiality

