8.0 Study Endpoints

8.1 Primary and Secondary Effectiveness Endpoints

The primary effectiveness endpoint is 30 day healing of the randomized groin incision, with any wound infection or failure to heal during that period representing an endpoint. All randomized patients will be followed out to 30 days regardless of developing an infection of the randomized groin incision

The secondary effectiveness endpoint is total hospital costs including 30 day readmission for treatment of infection of the randomized groin wound.

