9.0 Procedures Involved

9.1 Study Design

This is a prospective multicenter randomized double arm study to evaluate the prevention of groin wound infections in patients undergoing vascular surgery which requires ≥ 8 cm groin incision.

9.11 Randomization Plan:

We will employ a 1:1 randomization to either Prevena or Dermabond using a stratified blocked randomization plan with strata determined as a single incision or a bilateral incision with sequences of random block sizes of 4 or 8. Within the bilateral incision strata, one incision will be randomly chosen relative to defining a single endpoint measure, with site of incision essentially serving as a secondary substratum.

9.12 Statistical Analysis Plan Outline:

Primary Endpoint

The primary endpoint for this trial will be Szilagyi wound infection grade quantified on an ordinal scale (none, grade I: infection contained to the dermus, grade II: infection extending into the subcutaneous tissue but the arterial graft is not involved, grade III: infection of the arterial graft or native vessel underlying the incision). The primary analysis will be intent to treat and carried forth using an ordinal regression model with a stratified likelihood accounting for the primary randomization strata (incision number) and binary indicator variable for treatment arm with the primary test of treatment efficacy being the proportional odds different from 1. In the event of sparse data at the higher grades of infection (<2% at grade III), categories II and III will be combined. For the bilateral incision strata, the primary endpoint will be determined by randomly choosing a single incision as determined within the randomization scheme.

Secondary Endpoint

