The secondary endpoint will be a comparison of cost of treatment between the two arms and will be considered an exploratory analysis. We will utilize regression approaches to account for potential selection bias and censored cost endpoints. We have completed a preliminary appraisal of the additional per patient hospital costs (dispersed over the entire sample) for treating groin wound infections using the following assumptions. The associated wound infection rate for Prevena would be 6%.³ Groin wound infections for Prevena and Dermabond would require comparable care. Although lower wound severity grades have been reported for Prevena³ which could potentially decrease the complexity, duration and cost of subsequent treatment of wound infection for this group, the finding was not statistically significant.³ Therefore, we projected that treatment of groin wound infection in both groups would include an increased 10 day hospital length of stay,¹ seven days of IV antibiotics, daily CBC with or without differential and 2 cultures. We have estimated that the additional per patient cost of treating groin wounds if Prevena were used preemptively (\$935- \$1,114) would be similar to Dermabond (\$869- \$1,168) if the incidence of wound infection with Dermabond is $\leq 10\%$.

9.13 Sample size rationale:

Given $N=140=70+70$ total subjects and setting the Type I error rate = 0.05, we will have the power of 0.88 to detect a proportional odds of 4.9 different from 1. For our calculations, we assumed a probability vector for the ordinal scale (none, grade I, grade II, grade III) of (0.90, 0.08, 0.019, 0.001) for the Prevena treatment arm and (0.70, 0.16, 0.11, 0.03) for the Dermabond arm respectively. The power estimate was carried forth using 10,000 Monte Carlo simulations. This volume should be easily attainable over a 12 month period because on average 484 lower extremity revascularizations and 100 Abdominal Aortic Aneurysm Repairs are performed annually at Kaleida Health. While most of these procedures (85%) are completed by endovascular approach, access by groin cutdown is necessary in 25% of EVAR and 10% of EVI in addition to the planned open lower extremity revascularizations, which should allow for adequate numbers. SPSS 22 will be used to perform the statistical analysis.

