25.0 Provisions to Protect the Privacy Interests of Subjects

25.1 Steps to protect subject's privacy interest

At time of recruitment, potential subjects will be made aware of the need for study personnel to review their medical record, surgeon office record, vascular laboratory results for pertinent medical information following enrollment in the study through 30 days (25-40) following surgery but the review will be restricted to an as needed basis. Subjects will be informed of efforts to maintain confidentiality of protected health information. Only subjects who are agreeable to these terms will be enrolled. If during the study period, the subject wishes to restrict interaction with a particular study member or limit that individual's access to his/her protected health information and the situation can not be resolved, the subject should submit a written request to the PI. This will be noted in the subject's medical record and be included in his/her CRF. Every reasonable effort will be made to comply with the subjects request. If this is not feasible, the subject will be withdrawn from the study and missing data will be censored.

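### Section 19.3 permits randomization before the operation, although treatment, stratum and index groin depend on the incisions made; a patient left without an index incision has no analysis rule

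*Combined protocol and SAP*

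**What the plan says.** Section 19.3 lists where research procedures take place: "Patients may be screened for eligibility, consent obtained and randomized to a study arm in the surgeon's office", a hospital room or another private room. Its operating-room entry concerns product supply. Sections 3.2 and 5.1/5.2 mention consent and randomization together, with no interval or later step between them.

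The assigned treatment belongs to the operation. Section 13.3 states that "other than randomization to intra-operative wound treatment, all care will be provided in the standard fashion".

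Section 9.11, repeated under 11.1, stratifies with "strata determined as a single incision or a bilateral incision with sequences of random block sizes of 4 or 8". It does not say whether planned or actual incisions count. For bilateral cases, 9.11 says "one incision will be randomly chosen relative to defining a single endpoint measure", and 9.12 sets the primary endpoint by "randomly choosing a single incision as determined within the randomization scheme".

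The primary analysis in 9.12 is intention to treat on the Szilagyi grade of that one incision. Section 8.1 adds: "All randomized patients will be followed out to 30 days regardless of developing an infection of the randomized groin incision". Section 32.0 defines intention to treat as all participants, analysed as allocated. The only statement on handling missing data is in 25.1 and concerns a privacy request that cannot be met: "If this is not feasible, the subject will be withdrawn from the study and missing data will be censored".

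**The concern.** Three events can separate an early allocation from the operation performed: the operation is cancelled, the approach changes so that no groin is opened, or a planned bilateral case is done through one groin. In the first two there is no groin wound to grade. In the third, the outcome depends on how the index draw is read. If it is made among incisions that exist, the patient is gradable. If it is made together with an early allocation, the chosen groin may never have been opened.

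Such a patient remains in the intention-to-treat set, but the plan does not say whether to score grade none or to exclude. That choice would then be made after the data exist. Sections 13.1 to 13.4 and 25.1 deal with withdrawal, loss to follow-up and privacy restrictions, none of which is this case.

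Early allocation also lets the surgeon know the arm during the whole operation rather than only from closure onward.

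**Working it through.** **1. The plan's own figure.** Inputs from 9.13: 70 per arm, type I error 0.05 (taken as two-sided), grade probabilities (0.90, 0.08, 0.019, 0.001) for Prevena and (0.70, 0.16, 0.11, 0.03) for Dermabond; stated power 0.88. Simulation with the proportional-odds score test gives 0.886 (Wald 0.886, likelihood ratio 0.893). With grades II and III merged when grade III is below 2%, as 9.12 provides, the score test gives 0.885 to 0.89. The stated power reproduces.

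**2. Power when a share f has no index incision.** The documents give no f, so every value is an assumption, taken equal in both arms. If these patients are scored none, each arm's vector becomes (1 - f) × (stated vector) + f × (1, 0, 0, 0). If they are dropped, each arm keeps about 70 × (1 - f) patients.

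| f | Scored none | Dropped |
|---|---|---|
| 0 | 0.885-0.89 | 0.885-0.89 |
| 2.5% | 0.88 | 0.88 |
| 5% | 0.86-0.87 | 0.87 |
| 10% | 0.84 | 0.85 |
| 20% (stress case) | 0.78 | 0.80-0.81 |

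Repeat runs agree to within about 0.01.

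**3. Could it happen at all?** The chance of at least one such patient among 140 is 1 - (1 - f)^140: 0.50 at f = 0.5%, 0.76 at 1% and 0.97 at 2.5%.

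**4. Where a change of approach could arise.** Section 9.13 says "access by groin cutdown is necessary in 25% of EVAR and 10% of EVI in addition to the planned open lower extremity revascularizations". The cutdown share of the candidate pool depends on the base used:

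- Pool rebuilt from 9.13, with 85% endovascular in each procedure type. EVI cutdowns: 0.10 × (0.85 × 484) = 41.1. EVAR cutdowns: 0.25 × 85 = 21.3. Total 62.4. Open leg operations: 0.15 × 484 = 72.6. Share: 62.4 / 135.0 = 46%, or 62.4 / 150.0 = 42% with 15 open aneurysm repairs added.
- Same source, with all 100 aneurysm repairs taken as EVAR. Endovascular total: 0.85 × 584 = 496.4, so EVI = 396.4. Cutdowns: 25 + 39.6 = 64.6. Open leg operations: 0.15 × 584 = 87.6. Share: 64.6 / 152.2 = 42%.
- Section 20.2 gives about 204 candidates. Share: 62.4 / 204 = 31%. With the percentages applied to all procedures, (25 + 48.4) / 204 = 36%.

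So the share is 31% to 46%, and 9.13 and 20.2 do not agree on the pool. If 5%, 10% or 20% of planned cutdowns were abandoned (assumed) and open cases never were, the overall share would be 1.6-2.3%, 3.1-4.6% or 6.2-9.2%. That is about 2 to 13 of 140 patients. Reaching 20% overall by this route alone would need 0.20 / 0.46 = 43% to 0.20 / 0.31 = 65% of planned cutdowns to be abandoned.

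**5. Bilateral route, early-draw reading only.** The added share is (bilateral share) × (share converted to one groin) / 2. With an assumed 50% and 10%, this is 2.5%.

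**6. Stratum labels.** With 25% or 50% bilateral and 10% or 20% of those converted (assumed), planned rather than actual labels change power by at most 0.001 and type I error by less than 0.001.

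**The case against.** The strongest reply is that 19.3 lists locations and does not fix a time. It says patients may be randomized there, and its operating-room entry mentions keeping enough supply for randomization. The study flow diagram, where sequence would normally appear, was not visible in the text available for this review, and a few passages were also unavailable. This stands as a limit: if the diagram places allocation in the operating room, the defect is a conflict with 19.3 to be reconciled. It does not remove the point, because the available text permits early allocation and never defers it.

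The second reply is that eligibility keeps the number small. That also stands. Section 3.1 admits only elective procedures requiring a groin incision of at least 8 cm. A reader might take the 25% and 10% cutdown figures as rates of changed plans. They are not: they say how often a cutdown is needed, and no section says how often a planned one is abandoned.

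Third, following everyone, analysing as allocated and defining grade 0 as no signs of infection all lean towards scoring such a patient none. They lean that way but do not say it.

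Fourth, one sentence in 9.12 would close the endpoint gap, so moving the allocation is optional. That is correct for the endpoint. The later allocation is still the better method, because it prevents these cases and shortens the time during which the surgeon knows the arm.

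**Conclusion.** The point holds as a cheap improvement of minor to moderate severity. The plan allows allocation before the facts that define treatment, stratum and index groin exist, and it gives no rule for the few patients left without a gradable index incision.

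The size is modest. At an assumed 5% share power stays at 0.86-0.87, and at 10% at 0.84-0.85. These figures rest on the plan's grade probabilities and on equal shares in the two arms. The main cost is an avoidable choice after the data exist, not lost power.

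Three stronger readings are tempting, and the documents do not support them:

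- That 140 patients are too few. Power falls below 0.80 only when about 18% of patients (25 of 140) are affected and scored none, and nothing in the plan suggests such a share.
- That the surgeon's knowledge of the arm biases the result. It is possible, but the documents give no means of sizing it, and no bias is claimed.
- That a planned rather than actual stratum invalidates the stratified test. The calculation shows no measurable effect.

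**What to change.** Amend 9.11, 11.1 and 19.3 along these lines: *Consent is obtained before surgery. The concealed allocation is opened in the operating room after the groin incision or incisions are made and just before skin closure. Randomization is stratified on the number of groin incisions actually made; in bilateral cases the index groin is drawn among them.* Record patients consented but not randomized, with the reason, on the screening log in 23.2.

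Reconcile four items with this text:

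- the flow diagram, if it shows a different sequence;
- the patient and caretaker education in 9.3, which would be given to all consented patients beforehand or moved to after surgery;
- the irrigation step in 9.3, which refers to the randomized incision and so presumes that it is already identified;
- the study number, which 11.3 and 24.1 assign at randomization, so that consented but unrandomized patients would have none.

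For patients already randomized, or randomized in error, add to 9.12 and 11.1: *If only one groin was opened, it is the index incision. If no groin was opened, the patient stays in the intention-to-treat analysis as grade none, with exclusion as a sensitivity analysis; numbers are reported by arm.* If the allocation timing is left as it is, this text alone closes the endpoint gap, at no operational cost.

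The later allocation costs a wording amendment and one added step in the operating room at each of the two sites in 19.1. Section 19.3 says both products are already available there. It does not blind the surgeon at closure. The protocol is dated August 11, 2017, after the completion date of 05/31/17 in 7.3, so enrollment may have begun. If so, record the date of the change, because allocation timing and the basis of stratification would differ before and after it.
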